5.6.5 Documentation of Prior and Concomitant Medication Use

All medications administered during the study must be documented on the concomitant medication eCRF.

6 STUDY PROCEDURES

A 30-minute window for vital signs and all postdose procedures is allowed.

When multiple procedures are scheduled at the same time point, the order of procedures should be as follows: obtain vital signs, collect blood sample (drawn at nominal time), and obtain urine sample.

Blood samples for PK analysis can be obtained within ± 5 minutes of the scheduled sampling time for sample times ≤ 1 hour, within ± 10 minutes of the scheduled sampling time for sample times ≤ 12 hours, and within ± 2 hours of the scheduled sampling times for sample times > 12 hours.

6.1 Screening Visit (Days -21 to -1)

The following procedures will be performed at screening:

- Obtain informed consent;
- Evaluate inclusion/exclusion criteria;
- Obtain demographics and medical history;
- Record prior and concomitant medications;
- Perform physical examination including height and weight;
- Measure height and weight and calculate BMI;
- Record vital signs;
- Perform breath alcohol test;
- Collect urine sample for urine drug screen, cotinine, and urinalysis;
- Obtain fasting blood sample for safety laboratory tests, coagulation (activated partial thromboplastin time [aPTT], partial thromboplastin time [PTT], and international normalized ratio [INR]) serum (beta human chorionic gonadotropin [HCG]) pregnancy test (women of childbearing potential only), FSH (only for women of non-childbearing potential who are not surgically sterile), HIV, HBsAg, and HCVab screen; and
- Assess adverse events.

6.2 Check-in (Day -1)

The following procedures will be performed at Day -1:

- Admit subject to investigational site;
- Record prior and concomitant medications;
- Perform physical examination including weight for dose determination;
- Record vital signs;
- Perform breath alcohol test;

- Collect urine sample for urine drug screen, cotinine, urinary albumin, urinary creatinine, kidney injury molecule-1 (KIM-1), neutrophil gelatinase-associated lipocalin (NGAL) and urinalysis;
- Collect urine sample for pregnancy test women of childbearing potential only;
- Obtain fasting blood sample for safety laboratory tests; and
- Assess adverse events.

6.3 Treatment Period (Days 1 to 3)

6.3.1 Day 1

The following procedures will be performed on Day 1:

- Record prior and concomitant medications;
- Record vital signs (predose, 30 and 60 minutes and at 2, 4, and 12 hours after SC dosing);
- Collect urine sample for urinalysis predose;
- Obtain fasting blood sample for safety laboratory tests within 30 minutes prior to dosing;
- Administer study drug;
- Collect plasma PK samples (collected within 30 minutes prior to dosing, and at 30 minutes and 1, 2, 4, 6, 8, 10, 12, and 16 hours);
- Collect urine PK sample (within 60 to 30 minutes prior to dosing [spot sample] and between 0 to 4, 4 to 8, 8 to 12, 12 to 18, and 18 to 24 hours after dosing);
- Assess adverse events.

6.3.2 Day 2

The following procedures will be performed on Day 2:

- Record prior and concomitant medications;
- Perform physical examination;
- Record vital signs at 24 hours;
- Collect urine sample for urinary albumin, urinary creatinine, KIM-1, NGAL and urinalysis at 24 hours;
- Obtain fasting blood sample for safety laboratory tests at 24 hours;
- Collect plasma PK sample (24 and 30-36 hours after dosing);
- Collect urine PK sample (between 24 to 48 hours after dosing); and
- Assess adverse events.

6.3.3 Day 3

The following procedures will be performed on Day 3:

- Record prior and concomitant medications;
- Perform physical examination;
- Record vital signs at 48 hours;
- Collect urine sample for urinary albumin, urinary creatinine, KIM-1, NGAL and urinalysis at 48 hours;
- Collect plasma PK sample (48 hours after dosing);
- Collect urine PK sample up to 48 hours;
- Obtain fasting blood sample for safety laboratory tests at 48 hours;
- Assess adverse events; and
- Discharge subject from the investigational site.

6.4 Follow-up Visit (Day 8)

The following procedures will be performed at the Follow-up Visit on Day 8:

- Record prior and concomitant medications;
- Perform physical examination;
- Record vital signs;
- Collect urine sample for urinary albumin, urinary creatinine, KIM-1, NGAL and urinalysis;
- Obtain fasting blood sample for safety laboratory tests; and
- Assess adverse events.

6.5 Follow-up Visit (Day 15)

The following procedures will be performed at the Follow-up Visit on Day 15:

- Record prior and concomitant medications;
- Perform physical examination;
- Record vital signs;
- Collect urine sample for urinary albumin, urinary creatinine, KIM-1, NGAL and urinalysis;
- Obtain fasting blood sample for safety laboratory tests; and
- Assess adverse events.

6.6 Early Termination Visit and Withdrawal Procedures

The end of treatment for subjects completing the study is Day 15. For subjects who are withdrawn from the study prior to completion, the following procedures will be performed at the Early Termination Visit:

- Record prior and concomitant medications;

- Perform physical examination;
- Record vital signs;
- Collect urine sample for urinary albumin, urinary creatinine, KIM-1, NGAL and urinalysis;
- Obtain fasting blood sample for safety laboratory tests; and
- Assess adverse events.

7 PHARMACOKINETIC ASSESSMENTS

The actual PK blood sampling times will be captured on the eCRF. The actual dosing time will also be captured on the eCRF.

During the Treatment Period, plasma and urine samples will be collected for PK analysis. Plasma PK samples will be collected predose, at 30 min and 1, 2, 4, 6, 8, 10, 12, 16, 24, and 30-36 hours after SC injection, as well as on Day 3 (~48 hr). Blood samples for PK analysis can be obtained within ± 5 minutes of the scheduled sampling time for sample times ≤ 1 hour, within ± 10 minutes of the scheduled sampling time for sample times ≤ 12 hours, and within ± 2 hours of the scheduled sampling times for sample times > 12 hours.

Urine PK samples will be collected predose (spot sample) and between 0 to 4, 4 to 8, 8 to 12, 12 to 18, 18 to 24, and 24 to 48 hours after dosing.

7.1 Pharmacokinetic Parameters

Pharmacokinetic parameters will include the following:

- C_{\max} – maximum plasma concentration,
- t_{\max} – time to maximum plasma concentration,
- k_{el} – apparent terminal rate constant,
- $t_{1/2}$ – apparent elimination half-life,
- AUC_{0-t} – area under the concentration-time curve based on the last measureable concentration,
- AUC_{0-inf} – area under the concentration-time curve from time zero to infinity, and
- CL – clearance of study drug.

8 SAFETY ASSESSMENTS

8.1 Adverse Events

An adverse event is defined as any untoward medical occurrence in a clinical investigation subject administered a pharmaceutical product, which does not necessarily have a causal relationship with this treatment. An adverse event can therefore be any unfavorable and/or unintended sign (including an abnormal laboratory finding), symptom, or disease temporally associated with the use of an investigational medicinal product, whether or not related to the investigational medicinal product. All adverse events, including observed or volunteered problems, complaints, or symptoms, are to be recorded on the appropriate eCRF.

Adverse events, which include clinical laboratory test variables, will be monitored and documented from the time of informed consent until study participation is complete. Subjects should be instructed to report any adverse event that they experience to the Investigator. Beginning with the screening visit, the Investigator should make an assessment for adverse events at each visit and record the event on the appropriate adverse event eCRF.

Wherever possible, a specific disease or syndrome rather than individual associated signs and symptoms should be identified by the Investigator and recorded on the eCRF. However, if an observed or reported sign or symptom is not considered a component of a specific disease or syndrome by the Investigator, it should be recorded as a separate adverse event on the eCRF. Additionally, the condition that led to a medical or surgical procedure (eg, surgery, endoscopy, tooth extraction, or transfusion) should be recorded as an adverse event, not the procedure.

Any medical condition already present at screening should not be reported as an adverse event unless the medical condition or signs or symptoms present at baseline (pre-dose) changes in severity or seriousness at any time during the study. In this case, it should be reported as an adverse event.

Clinically significant abnormal laboratory or other examination findings that are detected during the study or are present at screening and significantly worsen during the study should be reported as adverse events. The Investigator will exercise his or her medical and scientific judgment in deciding whether an abnormal laboratory finding or other abnormal assessment is clinically significant. Clinically significant abnormal laboratory values occurring during the clinical study will be followed until repeat tests return to normal, stabilize, or are no longer clinically significant. Any abnormal test that is determined to be an error does not require reporting as an adverse event.

8.1.1 Adverse (Drug) Reaction

All noxious and unintended responses to a medicinal product related to any dose should be considered an adverse drug reaction. “Responses” to a medicinal product means that a causal relationship between a medicinal product and an adverse event is at least a reasonable possibility, (ie, the relationship cannot be ruled out).

8.1.2 Unexpected Adverse Drug Reaction

An unexpected adverse drug reaction is defined as an adverse reaction, the nature or severity of which is not consistent with the applicable product information in the Investigator’s Brochure.

8.1.3 Assessment of Adverse Events by the Investigator

The Investigator will assess the severity (intensity) of each adverse event as mild, moderate, or severe, and will also categorize each adverse event as to its potential relationship to study drug using the categories of yes or no.

The severity of all adverse events should be graded according to the Common Terminology Criteria for Adverse Events (CTCAE) Version 5.0. These criteria can be found at <http://ctep.cancer.gov/reporting/ctc.html>. For those adverse events not listed in the CTCAE, the following grading system should be used:

- Mild (CTCAE Grade 1): Transient symptoms, awareness of sign/symptom, but easily tolerated and no interference with subject's daily activities.
- Moderate (CTCAE Grade 2): Marked signs/symptoms that interfere with subject's usual activities, but still acceptable.
- Severe (CTCAE Grade 3): Incapacitating signs/symptoms which cause considerable interference with the subject's daily activities, unacceptable.
- Life-threatening (CTCAE Grade 4): Life threatening or disabling adverse event.
- Death (CTCAE Grade 5): Death-related adverse event.

Causality Assessment

The relationship of an adverse event to the administration of the study drug is to be assessed according to the following definitions:

No (unrelated, not related, no relation) – The time course between the administration of study drug and the occurrence or worsening of the adverse event rules out a causal relationship and another cause (concomitant drugs, therapies, complications, etc.) is suspected.

Yes (related) – The time course between the administration of study drug and the occurrence or worsening of the adverse event is consistent with a causal relationship and no other cause (concomitant drugs, therapies, complications, etc.) can be identified.

The definition implies a reasonable possibility of a causal relationship between the event and the study drug. This means that there are facts (evidence) or arguments to suggest a causal relationship.

The following factors should also be considered:

- The temporal sequence from study drug administration-
 - The event should occur after the study drug is given. The length of time from study drug exposure to event should be evaluated in the clinical context of the event.
- Underlying, concomitant, intercurrent diseases-
 - Each report should be evaluated in the context of the natural history and course of the disease being treated and any other disease the subject may have.
- Concomitant drug-
 - The other drugs the subject is taking or the treatment the subject receives should be examined to determine whether any of them might be recognized to cause the event in question.

- Known response pattern for this class of study drug-
 - Clinical and/or preclinical data may indicate whether a particular response is likely to be a class effect.
- Exposure to physical and/or mental stresses-
 - The exposure to stress might induce adverse changes in the recipient and provide a logical and better explanation for the event.
- The pharmacology and pharmacokinetics of the study drug-
 - The known pharmacologic properties (absorption, distribution, metabolism, and excretion) of the study drug should be considered.

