3 STUDY DESCRIPTION

3.1 Summary of Study Design

This is a Phase 1, open-label, single-ascending dose study to evaluate the safety, tolerability, and PK of OP-101 after SC administration in up to 8 healthy subjects at 1 site in Australia.

This study will consist of a 21-day Screening Period, a 2-day Treatment Period, and Follow-up Visits on Days 8 and 15. Subjects will sign an informed consent form (ICF) before any study procedures are performed and must meet all of the inclusion and none of the exclusion criteria to participate in the study. Eligible subjects will be admitted to the investigational site on Day -1, dosed on Day 1, and discharged on Day 3.

[figure not shown]
Figure 1 presents the cohort dosing schematic. There will be 2 separate and sequential SC cohorts (4 mg/kg and 8 mg/kg) with 4 subjects in each cohort who complete Day 15. Cohort 1 will enroll 4 subjects administered a single SC dose of 4 mg/kg. Dose escalation from Cohort 1 (4 mg/kg) to Cohort 2 (8 mg/kg) will be determined by the safety review committee (SRC), consisting of the Medical Monitor, the Principal Investigator (or delegate), and Sponsor representative after review of safety, tolerability, and any available PK data through Day 8 of Cohort 1. Cohort 2 will enroll 4 subjects administered a single SC dose of 8 mg/kg.

During the Treatment Period, plasma and urine samples will be collected for PK analysis. Plasma PK samples will be collected predose, at 30 minutes and at 1, 2, 4, 6, 8, 10, 12, 16, 24, and 30-36 hours after dosing, as well as on Day 3 (~48 hr). Blood samples for PK analysis can be obtained within ± 5 minutes of the scheduled sampling time for sample times ≤ 1 hour, within ± 10 minutes of the scheduled sampling time for sample times ≤ 12 hours, and within ± 2 hours of the scheduled sampling times for sample times > 12 hours.

Urine PK samples will be collected predose (spot sample) and between 0 to 4, 4 to 8, 8 to 12, 12 to 18, 18 to 24, and 24 to 48 hours.

Safety assessments will include adverse event monitoring, clinical laboratory tests (hematology, chemistry, and urinalysis), physical examinations, and vital signs (pulse rate, blood pressure [BP], respiration rate, and temperature). Coagulation testing will be performed at screening. Pregnancy testing will be performed at screening and Day -1.

Figure 1. OP-101 Single-Ascending Subcutaneous Dose Schedule – Day 1

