3.2 Study Stopping Rules

This study will stop and no further dosing and/or dose escalation will occur until safety information can be reviewed in the event that:

- 1 subject within a dose cohort has a drug-related Grade 3 adverse event or serious adverse event (SAE), or
- ≥ 2 subjects within the same dose cohort have a drug-related Grade 2 adverse event.

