#### ***7.4.1.2 Treatment-Emergent Adverse Event***

A TEAE is defined as an AE that emerges, having been absent prior to the study, or an AE that worsens in severity after the first dose of the study drug. Subjects reporting more than one adverse event for a given MedDRA preferred term will be counted only once for that term using the most severe incident. Subjects reporting more than one type of event within a system organ class (SOC) will be counted only once for that SOC. Safety population will be used for all the safety analysis.

TEAEs will be summarized by SOC and preferred term (PT) for each treatment and overall. The number and percentage of subjects experiencing TEAEs will be tabulated. Specifically, the following summaries will be presented:

- Overall summary of TEAEs by treatment and overall, with a breakdown by AE grading;
- TEAEs by SOC and PT by treatment;
- TEAEs by SOC, PT, and relationship to the study drug by treatment;
- TEAEs by SOC, PT, and maximum severity by treatment; and
- TEAEs by SOC, PT, maximum severity, and the relationship to the study drug by treatment.

Separate listings will be prepared for SAEs, AEs leading to deaths, and AEs leading to study discontinuation.

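### The yes/no causality definitions leave out events with fitting timing and another possible cause, and Yes is stricter than the protocol's own adverse-reaction standard

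*Protocol*

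**What the plan says.** Protocol 8.1.3 has the investigator classify each adverse event as related or not, with two categories and no default. For Yes, the time course "is consistent with a causal relationship and no other cause (concomitant drugs, therapies, complications, etc.) can be identified". For No, it "rules out a causal relationship and another cause (concomitant drugs, therapies, complications, etc.) is suspected". Directly after the Yes definition comes a broader sentence: "The definition implies a reasonable possibility of a causal relationship between the event and the study drug". A list of factors follows (intercurrent disease, concomitant drugs, stress and others), but it does not say how to code an event with two plausible causes.

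Protocol 8.1.1 sets a different threshold for an adverse drug reaction: that "a causal relationship between a medicinal product and an adverse event is at least a reasonable possibility, (ie, the relationship cannot be ruled out".

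Protocol 3.2 pauses the study if "1 subject within a dose cohort has a drug-related Grade 3 adverse event or serious adverse event (SAE), or" if at least "2 subjects within the same dose cohort have a drug-related Grade 2 adverse event".

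SAP 7.4.1 repeats the 8.1.3 definitions. SAP 7.4.1.2 plans five TEAE summaries. Two use relationship: "TEAEs by SOC, PT, and relationship to the study drug by treatment", and the one that crosses relationship with maximum severity.

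**The concern.** Each definition joins a timing condition to a condition on other causes, and the two are not complements. The commonest difficult case, plausible timing plus another candidate explanation, has no category, yet the investigator must choose one. The no-other-cause condition pushes towards No; the sentence on reasonable possibility and Section 8.1.1 push towards Yes.

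Such events are conceivable here. Protocol 1.2 reports proteinuria, granular casts and transient KIM-1 and NGAL rises after IV dosing, and asks for careful renal assessment. Section 5.6.4 allows nonsteroidal anti-inflammatory drugs case by case. A renal finding in a subject who had received one could have a second candidate cause, and would then fail the literal Yes.

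Relatedness bears on stopping triggers in cohorts of 4, where recoding one subject can decide the outcome, and on tables that serve the primary objective. It also decides which SAEs must be reported after the 30-day period (Protocol 8.3). The study is open-label without a control group, so no concurrent comparison can make up for unclear attribution.

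**Working it through.** **Step 1: are the definitions exhaustive?** Cross the two conditions in 8.1.3.

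| Timing | Other cause | Category under 8.1.3 |
|---|---|---|
| Consistent | None identified | Yes |
| Consistent | Present | Neither |
| Ruled out | Present | No |
| Ruled out | None identified | Neither |

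Two of the four combinations have no category. The last row matters little, since such events would naturally be coded No. The second row is the problem.

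**Step 2: compare with 8.1.1.** A second-row event has timing that does not exclude the drug. Where the relationship cannot be ruled out, 8.1.1 makes it an adverse drug reaction, yet it fails Yes because another cause can be identified. The literal Yes is therefore narrower than the protocol's own standard. The reasonable-possibility sentence signals a broader intent but does not remove the no-other-cause condition.

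**Step 3: possible effect on the triggers.** The documents give no event rates and no share of mixed events, so there is no planned figure to reproduce. What follows is illustrative.

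- n = 4 per cohort (Protocol 9.3); thresholds of at least 1 subject (Grade 3) and at least 2 subjects (Grade 2) from Protocol 3.2.
- p = assumed per-subject probability of a truly related event of that grade, with subjects independent.
- m = assumed share of truly related events coded No; m = 0 if every mixed event is coded Yes.
- q = p(1 − m).

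Grade 3 trigger: 1 − (1 − q)^4. 
Grade 2 trigger: 1 − (1 − q)^4 − 4q(1 − q)^3.

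For example, with p = 0.10 and m = 0.5, q = 0.05. The Grade 3 chance is 1 − 0.95^4 = 0.1855, against 1 − 0.90^4 = 0.3439 at m = 0.

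| Trigger | p | m = 0 | m = 0.25 | m = 0.5 |
|---|---|---|---|---|
| Grade 2 | 5% | 1.4% | 0.8% | 0.4% |
| Grade 2 | 10% | 5.2% | 3.0% | 1.4% |
| Grade 2 | 30% | 34.8% | 22.0% | 11.0% |
| Grade 3 | 5% | 18.5% | 14.2% | 9.6% |
| Grade 3 | 10% | 34.4% | 26.8% | 18.5% |
| Grade 3 | 20% | 59.0% | 47.8% | 34.4% |

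These are chances that a trigger is met over a complete cohort. They do not measure protection lost. The SAE trigger is affected only if the drug-related qualifier in 3.2 also applies to serious adverse events, which the sentence leaves open.

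**The case against.** The best reply accepts the gap in the wording and disputes its consequences.

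- **The text leans towards Yes.** A mixed event fails No outright, because its timing does not exclude the drug, and two passages favour Yes. This is fair, and if every mixed event were coded Yes there would be no loss. But the no-other-cause condition remains, and an investigator who codes No can rely on it.
- **Mixed events should be few.** Subjects are healthy, medication is restricted, they are in-house from Day -1 to Day 3, and Protocol 5.2 reports no clinical adverse events at 20 or 40 mg/kg IV. This stands. Nothing in the documents supports m = 0.25 or 0.5, and m = 0.5 needs at least half of all truly related events to be mixed. The higher assumed event rates have no support in the documents either.
- **Other protections exist.** The SRC decides on escalation "after review of safety, tolerability, and any available PK data through Day 8 of Cohort 1", which is not limited to related events. SAEs up to 30 days are reported within 24 hours whatever their cause, withdrawal criteria do not depend on relatedness, and three of the five TEAE summaries ignore it. This stands for Cohort 1. No SRC review is described during Cohort 2 dosing, so the triggers carry more weight there. Even so, Cohort 2 is the last cohort with single doses, and a stop can protect only subjects not yet dosed.
- **One site, and completion procedures not seen.** Protocol 11.4 has the sponsor review eCRF procedures with site staff before enrolment. Those procedures might settle the matter, but the protocol and SAP do not.
- **Section 3.2 does not cite 8.1.3.** True: the link is an inference. But 8.1.3 is the only causality classification the protocol asks the investigator to make. If 8.1.1 governed the triggers instead, the stopping rule and the recorded data would follow different standards.

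**Conclusion.** The definitions are wrong as written and should be fixed. That they are incomplete, and that the literal Yes is stricter than Section 8.1.1, follows from the text alone and needs no assumption. That drug-related counts may be too low is conditional: it requires mixed events to occur and to be coded No. The size is unknown, could be zero, and is probably limited by the healthy population, the medication restrictions and the SRC review of Cohort 1. The percentages above rest on assumed rates, assumed miscoding shares and independence between subjects, and serve only to show that cohorts of 4 are sensitive to recoding.

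**What to change.** In Protocol 8.1.3 and SAP 7.4.1, make the two categories complementary on the 8.1.1 threshold:

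- **Yes:** a causal relationship is a reasonable possibility and cannot be excluded, whether or not another possible cause exists.
- **No:** every other event.

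Record alternative causes as a factor in the judgement, not as a condition that blocks Yes. Make clear that the drug-related qualifier in Section 3.2 uses this definition, and whether it applies to SAEs.

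The cost is a protocol amendment with the full review and ethics committee approval required by Section 12.1, a matching SAP edit and brief site training. Somewhat more events will be labelled related, so the triggers may be met somewhat more often. That errs on the cautious side, since Section 3.2 halts dosing only pending a safety review.

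A separate correction, which carries no weight in this finding, can go into the same SAP edit: SAP 7.4.1 cites CTCAE version 4.0, while Protocol 8.1.3 specifies 5.0.
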